Cognitive Outcomes. Four cognitive-behavioral measures that evaluate impulsive behavior will be included and will be completed 20 minutes after administration of the sampling dose. These tasks were selected because: (i) cocaine users display increased impulsive behavior (Coffey et al., 2003; Fillmore and [name], 2002; Heil et al., 2006; Liu et al., 2011) which likely contributes to poor treatment response and relapse (Dalley et al., 2011; Poling et al., 2007) and (ii) 5-HT systems are strongly implicated in impulsive behavior (Brunner and Hen, 1997; Cunningham and Anastasio, 2014; Howell and Cunningham, 2015). The selected tasks measure three key, independent aspects of impulsivity: impulsive decision-making (i.e., delay discounting for money and cocaine), impulsive inattention (i.e., n-Back), and impulsive disinhibition (i.e., go/stop task) (Reynolds et al., 2008). Tasks will be completed in random order across subjects, but the order of tasks will remain consistent for each subject.

Hypothetical Delay Discounting (Appendix B). A 5-trial adjusting delay discounting task will be used to rapidly assess discounting rates for various commodities (Koffarnus and Bickel, 2014). In this task, subjects making a series of 5 choices between an immediately available, smaller reinforcer and a larger reinforcer at various delays. Versions of this task with monetary (e.g., \$1000 delayed versus \$500 now) and cocaine (e.g., \$1000 of cocaine delayed versus \$500 of cocaine now) commodities will be used. Subjects will be told that all choices are hypothetical. The primary outcome of this task is the discounting rate (k). Previous research has demonstrated that this measure provides rapid and accurate discounting rates across a range of commodities (Cox and Dallery, 2016; Koffarnus and Bickel, 2014; Strickland et al., 2017).

n-Back (Appendix C). The n-Back task will be used to measure working memory and working memory capacity (Jaeggi et al. 2010). In this task, subjects are presented with a sequence of numbers and asked to indicate when the current stimulus matches the one from “n” steps earlier. Two settings will be used in this study, the 1-back and the 2-back (i.e., matching 1 and 2 stimuli back, respectively). The primary outcome of this task is the percentage of correct responses.

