Aim 2: Demonstrate that 5-HT_{1b} activation attenuates subjective abuse-related effects of cocaine (e.g., positive subjective effects, craving). Three sets of analyses will be conducted on the subjective effect data. First, data will be analyzed as peak effect (i.e., maximum effect observed following administration of cocaine sampling doses) using two-factor repeated-measures ANOVA. Cocaine (0, 10, and 30 mg/70 kg) and zolmitriptan (0, 2.5, 5, and 10 mg/day) will be factors for these analyses. A significant augmentation or attenuation of the effects of cocaine will be inferred if the main effect of the zolmitriptan or the cocaine-zolmitriptan interaction attains statistical significance in the ANOVA. If the cocaine-zolmitriptan interaction attains statistical significance, the MSE term will be used to conduct Tukey's HSD *post-hoc* test to make appropriate pair-wise comparisons between means. Second, Area Under the Curve (AUC) will be calculated for each subject using the trapezoidal method and analyzed in the same fashion as peak-effect data. Third, these data will be analyzed by repeated-measure ANOVA with cocaine, zolmitriptan and time as factors. The MSE term for the cocaine-zolmitriptan-time interaction will then be used to conduct Tukey's *post-hoc* tests to make appropriate pair-wise comparisons.

Aim 3: Demonstrate that 5-HT_{1b} activation attenuates impulsive responding that is a common characteristic of cocaine use disorder and is mediated by the 5-HT system. For the impulsivity outcomes, each of which have only one data point for each dose condition, data will be analyzed using two-factor repeated-measures ANOVA. Cocaine (0, 10, and 30 mg/70 kg) and zolmitriptan (0, 2.5, 5, and 10 mg/day) will be factors for these analyses. A significant augmentation or attenuation of the effects of cocaine will be inferred if the main effect of the zolmitriptan or the cocaine-zolmitriptan interaction attains statistical significance in the ANOVA. If the cocaine-zolmitriptan interaction attains statistical significance, the MSE term will be used to conduct Tukey's HSD *post-hoc* test to make appropriate pair-wise comparisons between means.

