9. POTENTIAL RISKS

The behavioral and physiological assessment procedures employed in this study are benign. The risks to the study subjects are those related to the administration of the drugs under study. Cocaine has safely been administered to human subjects under controlled-laboratory conditions. The relative safety, as well as the contraindications and possible side effects of cocaine and zolmitriptan are well known and documented. However, the administration of any drug involves some risks simply because individuals differ in their reactions

to drugs. The main risk is that subjects will experience side effects that may be unpleasant. The side effects of zolmitriptan and cocaine may change as a function of the drug combinations, which is why we will not be dosing more than the recommended daily amount of zolmitriptan (i.e., 10 mg/day) in this study.

Common side effects of zolmitriptan include dry mouth, nausea, pain/pressure in neck or throat, drowsiness, weakness, warmth, redness or mild tingling under the skin, increased heart rate and increased blood pressure. More serious side effects include chest pain, sudden lateral numbness or weakness, sudden headache, confusion, problems with vision, speech or balance, dizziness, severe stomach pain, hematochezia, serotonin syndrome and cyanosis.

Common side effects of cocaine include anxiety, restlessness, diuresis, irritability, suppressed appetite, insomnia, gastrointestinal upset, increased heart rate, increased blood pressure, palpitations, and arrhythmias. More serious side effects following the chronic, unsupervised administration of much higher doses of cocaine have occurred and include psychotic episodes, suppressed breathing, seizures, myocardial infarctions, heart failure and death.

The doses to be administered in the present experiment were chosen to minimize, if not eliminate, the chance of these side effects occurring since these side effects are related to dose. Thus, it is unlikely that subjects will experience side effects during the experimental protocol. All experiments proposed in this application will be conducted at the CRU and under medical supervision. Side effects of the drugs are temporary, usually dissipating in less than 24 hours.

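### The only n-Back score, percentage of correct responses, mixes discrimination with willingness to respond; scoring d' for each load would be a cheap improvement to this secondary Aim 3 outcome

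*Combined protocol and SAP*

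**What the plan says.** Section 7 (Cognitive Outcomes) lists the aspects of impulsivity to be measured and assigns one of them to this task: "impulsive inattention (i.e., n-Back"). The n-Back paragraph also describes the task as a measure of working memory. Subjects see a sequence of numbers and are "asked to indicate when the current stimulus matches the one from" n steps earlier. On load it says: "Two settings will be used in this study, the 1-back and the 2-back". On scoring it says only: "The primary outcome of this task is the percentage of correct responses". No false-alarm rate, d', criterion or omission count is specified for the task.

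Under Data Analysis, Aim 3, the plan speaks of the impulsivity outcomes, "each of which have only one data point for each dose condition", and enters them into a two-factor repeated-measures ANOVA. The inference rule begins: "A significant augmentation or attenuation of the effects of cocaine will be inferred if the main effect of the zolmitriptan or the cocaine-zolmitriptan interaction" reaches significance. A zolmitriptan main effect on the n-Back score would therefore be enough.

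Section 9 states: "Common side effects of zolmitriptan include dry mouth, nausea, pain/pressure in neck or throat, drowsiness, weakness". Section 17 places cognitive effects among the secondary outcomes.

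**The concern.** In a match-detection task, a subject's score depends on two things: discrimination and the criterion for responding. If percentage correct means hits, a subject who presses on every item scores 100%. If it means accuracy over all items, holding back is rewarded when non-matches clearly outnumber matches. If it means the share of presses that are correct, holding back is rewarded again.

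Zolmitriptan could plausibly change readiness to respond, since drowsiness and weakness are listed as common effects. A zolmitriptan main effect on the score could then be reported as a change in impulsive inattention when only the criterion had moved, and its sign would depend on a scoring choice the plan does not state. The same section handles this better for the Stop-Signal Task, where response execution (go reaction time) is scored apart from inhibitory failures.

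**Working it through.** The documents state no n-Back figure, so there is none to reproduce. The check asks how far each reading of the score moves when discrimination is held fixed.

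**From the documents:** subjects signal matches; one score, percentage correct; two loads; a zolmitriptan main effect suffices for inference.

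**Assumed, because the documents do not give them:** an equal-variance normal signal-detection model; d' of 1.5, 2 or 3; match share p of 20%, 30% or 50%; criterion c moved from 0 to 0.5 (less willing to respond).

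**Formulas**

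- Hit rate H = Φ(d'/2 − c)
- False-alarm rate FA = Φ(−d'/2 − c)
- All-item accuracy = pH + (1 − p)(1 − FA)
- Share of presses that are correct = pH / [pH + (1 − p)FA]

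**Central case, d' = 2, p = 0.30**

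- c = 0: H = Φ(1) = 0.841 and FA = Φ(−1) = 0.159. Accuracy = 0.3 × 0.841 + 0.7 × 0.841 = 0.841. Correct presses = 0.252 / (0.252 + 0.111) = 0.694.
- c = 0.5: H = Φ(0.5) = 0.691 and FA = Φ(−1.5) = 0.067. Accuracy = 0.3 × 0.691 + 0.7 × 0.933 = 0.861. Correct presses = 0.207 / (0.207 + 0.047) = 0.816, before rounding of the parts.

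| Reading of the score | c = 0 | c = 0.5 | Apparent direction |
|---|---|---|---|
| Hits | 84.1% | 69.1% | worse |
| All-item accuracy | 84.1% | 86.1% | slightly better |
| Correct presses | 69.4% | 81.6% | better |
| d' = z(H) − z(FA) | 2.00 | 2.00 | unchanged |

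**Range over the assumed grid, same shift in c.** Hits fall by about 9 to 17 points. All-item accuracy changes by −2.9 to +6.2 points: it rises when matches are 20% or 30% of items and falls when they are 50%. Correct presses rise by about 4 to 15 points. At d' = 3 and 30% matches, all-item accuracy barely moves (93.3% to 93.6%).

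**False-alarm rate.** In the central case it falls from 15.9% to 6.7% with d' unchanged. For a larger shift, c from −0.6 to +0.6 at d' = 2, it falls from 34% to 5%. It is no freer of criterion than percentage correct.

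**Limit of d'.** Suppose a drowsy subject makes no response on a random 20% of items, starting from d' = 2 and c = 0. Then H = 0.8 × 0.841 = 0.673, FA = 0.8 × 0.159 = 0.127, and apparent d' = z(0.673) − z(0.127) = 1.59. So d' is unaffected by a pure criterion shift, but not by lapses.

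**The case against.** The strongest reply is that d', criterion and match share are all assumed, and that all-item accuracy, a natural reading of the score, is nearly flat around a neutral criterion. That stands as a limit on size: under that reading the effect may be negligible. It does not settle which reading applies, and the hits and correct-press readings move in opposite directions throughout the grid.

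Second, a reader might infer that zolmitriptan drowsiness will be misread as a change in impulsivity with discrimination intact. The documents do not support that. Section 9 lists drowsiness without a rate, and nothing says that it acts through criterion rather than discrimination. Section 7 also adds 1.5 days of maintenance so that transient side effects can fade before sessions.

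Third, a reader might infer that the n-Back result could not be interpreted at all. That is too strong. Sleepy, drowsy and fatigued ratings (Appendix A) are taken before the sampling dose and every 15 minutes after it, around the cognitive tasks at 20 minutes. Go reaction time comes from the same battery, the UKU covers sedation daily, and each zolmitriptan condition includes a 0 mg cocaine session. These allow a sedation explanation to be examined, although the plan ties none of them to the n-Back analysis and none separates criterion from discrimination within the task.

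Fourth, disinhibited responding is assigned to the stop task, so the n-Back need not be scored as a measure of impulsive pressing. That stands, and it is a further reason not to promote the false-alarm rate to an impulsivity outcome.

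Finally, the Appendix C diagram is not shown in the text available here and may give the response format. A forced match/non-match key would remove the point about withholding presses, but bias between the two keys would remain possible.

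**Conclusion.** The point holds as a modest improvement to one secondary outcome. As written, the n-Back score cannot separate discrimination from willingness to respond, and under a pure criterion shift its direction depends on a definition the plan leaves open. In the central case the same behaviour reads as a 15-point loss, a 2-point gain or a 12-point gain. Those sizes rest on the equal-variance model and on assumed d', criterion and match share; for all-item accuracy the change can be near zero. Whether zolmitriptan shifts the criterion at all is not known from the documents. The primary break-point analysis does not depend on this.

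**What to change.** Before unblinding, amend the n-Back paragraph and the Aim 3 analysis as follows.

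- For the 1-back and 2-back separately, make d' the n-Back outcome, computed from hits and false alarms with a log-linear correction for rates of 0 or 1. This also settles how two loads fit a plan that speaks of one value per dose condition.
- Report hit rate, false-alarm rate and criterion beside d'. Do not treat the false-alarm rate alone as an impulsivity outcome.
- Keep percentage correct as descriptive, with its numerator and denominator stated.
- Say that any zolmitriptan effect on d' will be read with the drowsiness ratings and go reaction time already collected, since lapses can lower d'.

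The cost is re-scoring computer-collected responses, with a few more scores per load to report. Section 7 says the laptop records and stores each subject's data; the sponsor should confirm that this includes item-level responses, without which hits and false alarms may not be recoverable. No study procedure changes.

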Stop-Signal Task. Letters (X or O) will be presented on the screen one at a time and participants are instructed to respond on the computer keyboard to identify the letter that was presented. On approximately 30% of trials a stop-signal tone (a 500 ms, 900 Hz tone) will occur, and participants must withhold their response (50 trials). The tone will be random and will occur at one of five delays (10, 70, 150, 230, or 300 ms; stop-signal delay) after the presentation of the letter. The presentation of the stop-signal is divided evenly between letters. Participants are instructed to respond as quickly as possible to letters and not to wait for the tone to occur. The dependent variables from the stop-signal task are the mean proportion of inhibitory failures to the stop-signal and by the estimated mean latency to inhibit a response. The mean RT to the go-signals (i.e., responding to the letters, not in the presence of the stop-signal) will measure response execution to go-signals during a test (i.e. the average time from the onset of letter presentation until a computer key press). Shorter reaction times (i.e. faster responding) indicate greater response execution. The inhibition and execution measures are highly reliable across trials (alpha coefficients >0.90) and stable over sessions (test-retest reliabilities >0.85) in both drug-using and non-drug-using populations (Fillmore and [name], 2001; Fillmore and Vogel-Sprott, 1999; Mulvihill et al., 1997). The order of letters, stop-signal, and stop-signal delays will be random.

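### The stop-signal failure proportion mixes go speed with stopping speed, and Aim 3 does not rank it against stop latency or say how discordant results are read

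*Combined protocol and SAP*

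**What the plan says.** All references are to the combined protocol and SAP.

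- **Task (section 7, Stop-Signal Task).** "On approximately 30% of trials a stop-signal tone" sounds, and on those trials "participants must withhold their response (50 trials" in number). On timing: "The tone will be random and will occur at one of five delays (10, 70, 150, 230, or 300 ms; stop-signal delay"). No rule adapts the delay to the subject's speed.
- **Outcomes (same place).** "The dependent variables from the stop-signal task are the mean proportion of inhibitory failures to the stop-signal", and also performance as indexed "by the estimated mean latency to inhibit a response". Mean go reaction time is recorded too, and it "will measure response execution to go-signals during a test". The estimation method for the latency is not given.
- **Ranking.** Section 7 names one primary outcome for delay discounting (the rate k) and one for the n-Back (percentage correct). It names none for the stop-signal task.
- **Inference (section 7, Data Analysis, Aim 3).** Each impulsivity outcome goes into a cocaine-by-zolmitriptan repeated-measures ANOVA. "A significant augmentation or attenuation of the effects of cocaine will be inferred if the main effect of the zolmitriptan", or its interaction with cocaine, is significant.
- **Direction (section 1, Aim 3).** Zolmitriptan is expected to reduce impulsive responding.
- **Side effects (section 9).** The common zolmitriptan effects include "pain/pressure in neck or throat, drowsiness, weakness".
- **Status (section 17, Data Monitoring Plan).** Cognitive effects are secondary outcomes; break points are primary.

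**The concern.** On a stop trial the subject fails when the go response finishes before the stop process does. With a fixed delay, a slower go response gives the stop process more time to win, so failures fall even if stopping is no faster. A drug that makes people sluggish can therefore improve the failure proportion.

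That movement is in the direction Aim 3 predicts, and the failure proportion alone cannot show which process moved. The Aim 3 rule applies to impulsivity outcomes in general, with no condition on go speed. If failures fall and stop latency does not, the plan leaves the team to decide after seeing the data which variable stands for disinhibition. At stake is a secondary claim that zolmitriptan reduces impulsive disinhibition.

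**Working it through.** **1. The plan's own design figure.** The only one that bears on sensitivity is f = 0.27 at 80% power with 20 completers (section 7, Power Analysis). A noncentral F test with n = 20, four zolmitriptan levels, correlation 0.5 and sphericity gives power 0.799 at f = 0.27, so the figure reproduces. The correlation and sphericity are assumptions, since the documents state neither. The plan gives no figure for the stop-signal task.

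**2. Trial counts.** 50 stop trials / 0.30 = about 167 trials, which leaves about 117 go trials. An even split over delays (assumed) gives 50 / 5 = 10 stop trials per delay.

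**3. Race model.** Let go time be normal with mean m and SD s, and stop latency have mean L and SD 40 ms. Then

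P(fail at delay d) = Φ[(d + L − m) / √(s² + 40²)],

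averaged over d = 10, 70, 150, 230 and 300 ms. The delays come from the protocol. The values of m, s, L and the 40 ms are assumptions.

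Worked case: m = 400, L = 250, s = 80, so the denominator is √(6400 + 1600) = 89.4.

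- Before slowing, the five probabilities are 0.059, 0.186, 0.500, 0.814 and 0.953; mean 0.502.
- With m = 430 they are 0.029, 0.109, 0.369, 0.712 and 0.910; mean 0.426.
- The change is −0.077 before rounding.

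Only L − m enters the formula. Slowing go responses by 30 ms therefore lowers failures exactly as much as a true 30 ms gain in stopping speed.

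**4. Range for 30 ms of go slowing, L unchanged, s from 80 to 120 ms.**

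| Go time m | Stop latency L | Failures before | Failures after | Change |
|---|---|---|---|---|
| 400 | 200 | 0.376–0.389 | 0.302–0.323 | −0.065 to −0.073 |
| 400 | 250 | 0.502–0.503 | 0.426–0.434 | −0.069 to −0.077 |
| 500 | 200 | 0.154–0.191 | 0.105–0.145 | −0.046 to −0.049 |
| 500 | 250 | 0.256–0.282 | 0.192–0.225 | −0.057 to −0.064 |
| 600 | 200 | 0.033–0.067 | 0.017–0.045 | −0.015 to −0.022 |
| 600 | 250 | 0.078–0.118 | 0.048–0.085 | −0.031 to −0.033 |

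A skewed (ex-Gaussian) go distribution gives a similar picture: −0.047 to −0.078 over go times of 350 to 500 ms and latencies of 180 to 260 ms, shrinking to −0.009 at 600 and 180 ms.

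**5. If stopping slows too.** In the worked case, a 15 ms rise in L alongside the 30 ms go slowing cuts the change from −0.077 to −0.038. A 30 ms rise removes it entirely.

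**6. Simulated trials, true stop latency unchanged.** 20 subjects, 3 × 4 cells, 400 replicates, slowing graded by dose up to the value shown. Go times are ex-Gaussian with mean 450 (sigma 50, tau 70), between-subject SD 50 and session SD 15 ms; latency is 220 ms. Stop latency is estimated by the integration method at each delay. Entries are the share of trials with a significant zolmitriptan main effect.

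| Top-dose slowing | Failure proportion | Stop latency | Go time |
|---|---|---|---|
| 0 ms | 0.05 | 0.03 | 0.04 |
| 10 ms | 0.33 | 0.05 | 0.80 |
| 20 ms | 0.90 | 0.04 | 1.00 |
| 30 ms | 1.00 | 0.07 | 1.00 |
| 20 ms, session SD 25 | 0.76 | 0.04 | 0.98 |
| 20 ms, session SD 40 | 0.49 | 0.05 | 0.64 |

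Two further simulations under other assumptions gave 47% and about 70% for failures at 20 ms, and 83% and about 96% at 30 ms. Stop latency was significant in about 3–8% and 7–9% of trials respectively. Stop latency is not fully immune: at 60 ms of slowing one simulation rejected in 13% of trials.

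**The case against.** The strongest reply is that the plan already collects what is needed. The outcome sentence goes on to name the estimated latency to inhibit, and go time is measured in every session. In the simulations go time usually revealed the slowing and stop latency stayed close to its nominal error rate. A careful analyst would see the artefact. Sedation is also tracked by the daily UKU and by questionnaire items on drowsiness, tiredness and sluggishness. Section 7 (Drug Dose and Administration) adds 1.5 maintenance days so that transient zolmitriptan effects can pass. All of this stands. The instruction to respond quickly and not wait for the tone also helps, but it targets deliberate waiting rather than drug-related slowing.

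Two stronger readings are tempting. One is that the plan *will* read slowing as reduced disinhibition. The documents do not say so: they set no rule for discordant results, so the most one can say is that it could be read that way. The other is that a sedating dose by itself produces the Aim 3 result. That requires going to slow more than stopping, and nothing in the documents shows that it does; step 5 shows the artefact vanishing when both slow equally.

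The magnitudes are also illustrative. Go times, latencies, noise and the size of slowing appear nowhere in the documents, and the effect is small near the floor.

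What the reply does not answer is the lack of ranking. Collecting the diagnostic data does not say which variable carries the inference.

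**Conclusion.** The concern holds in a limited form. Of the two stop-signal variables, the failure proportion is confounded with go speed because the delays are fixed. The Aim 3 rule can be met by that variable, and the plan gives neither a hierarchy, nor a method for estimating stop latency, nor a reading for discordant results.

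With stop latency held constant, 30 ms of slowing lowers failures by about 0.015 to 0.077. With 20 ms at the top dose, the failure proportion reaches significance in about 47% to 90% of simulated trials, against roughly 3% to 9% for stop latency. These figures rest on the race model, on assumed response times and noise, and on stopping being unaffected. They show that the mechanism can matter at this sample size, not how likely it is to occur.

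The primary break-point result is untouched. A change is worth making because it is cheap and settles a choice that would otherwise be made after the results are known.

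**What to change.** In section 7, under Stop-Signal Task and under Data Analysis for Aim 3:

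- Name the estimated latency to inhibit as the stop-signal outcome to which the Aim 3 inference rule applies. State the method: integration, computed per session from go times, delays and failure proportions.
- Report the failure proportion by delay, and mean go time, as supporting data.
- State in advance that fewer failures with slower go responses and unchanged stop latency is not evidence of attenuated impulsivity.

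The task, schedule and data collection stay as they are, so the cost is wording. The statistical cost is that stop latency is noisier per session than a raw proportion and is unstable for a subject with almost no failures. The plan should therefore say how such sessions are handled.
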